
LIST OF ABBREVIATIONS AND DEFINITION OF TERMS

Abbreviation	Definition
AE	Adverse event
AESI	Adverse event of special interest
ALT	Alanine aminotransferase
AML	Acute myeloid leukemia
AST	Aspartate aminotransferase
ATC	Anatomic therapeutic class
AUClast	Area under the concentration time curve from time = 0 to the time of the last quantifiable concentration
AUCinf	Area under the concentration time curve from time = 0 extrapolated to infinity
AUMClast	Area under the first moment of the concentration-time curve from time =0 to the time of the last quantifiable concentration
BLQ	Below the limit of quantification
C	Cycle
CI	Confidence interval
CL	Total body clearance
CLS	Capillary leak syndrome
Cmax	Maximum observed concentration
CMML	Chronic Myelomonocytic Leukemia
CR	Complete response
CSR	Clinical study report
CT	Computed tomography
CTCAE	Common Terminology Criteria for Adverse Events
D	Day
DLT	Dose-limiting toxicity
DO R	Duration of response
ECOG PS	Eastern Cooperative Oncology Group Performance Status
ECG	Electrocardiogram
eCRF	Electronic case report form
ELN	European Leukemia Net
hIL-3	Human interleukin-3
HMA	Hypomethylating agents
HU	Hydroxyurea
IL-3R	Interleukin-3 Receptor
IWG	International Working Group
IWG-MRT	International Working Group Myeloproliferative Neoplasms Research
IV	Intravenous

Abbreviation	Definition
λ_z	First order terminal elimination rate constant
MDS	Myelodysplastic syndrome
MedDRA	Medical Dictionary for Regulatory Activities
MF	Myelofibrosis
mITT	Modified intent-to-treat
MPN	Myeloproliferative neoplasm
MPN-SAF-TSS	Myeloproliferative Neoplasm Symptom Assessment Form Total Symptom Score
MRI	Magnetic resonance imaging
MRT _{inf} IV	Mean residence time extrapolated to infinity
MTD	Maximum tolerated dose
MTeD	Maximum tested dose
NCA	Non-compartmental analysis
ORR	Objective response rate
OS	Overall survival
PCS	Potentially clinically significant
pDC	Plasmacytoid dendritic cell
PD	Progressive disease
PED	Primary Eosinophilic Disorders
PFS	Progression-free survival
PK	Pharmacokinetic
PP	Per-Protocol
PR	Partial response
PT	Preferred term
Rel Day	Relative study day
RP2D	Recommended phase 2 dose
SAE	Serious adverse event
SAP	Statistical analysis plan
SCT	Stem Cell Transplant
SD	Stable disease
SM	Systemic Mastocytosis
SMQ	Standardized Medical Query
SOC	System organ class
$t_{1/2}$	Terminal elimination half-life
TEAE	Treatment-emergent adverse event
TI	Infusion duration
t _{last}	Time of last quantifiable concentration
t _{max}	Time of first occurrence of C _{max}

Abbreviation	Definition
Vss	Steady-state volume of distribution
Vz	Volume of distribution during the terminal disposition phase
WHO	World Health Organization

1. INFORMATION FROM THE STUDY PROTOCOL

1.1. Introduction and Objectives

1.1.1. Introduction

Certain subtypes of myeloproliferative neoplasms (MPNs) and myelodysplastic syndrome (MDS)/MPNs represent clonal proliferations arising from malignant myeloid stem cells with propensity to overexpress interleukin-3 receptor (IL-3R), rendering them potentially susceptible to tagraxofusp. MPNs are associated with considerable morbidity and mortality, and risk of transformation to acute myeloid leukemia (AML). The substantial IL-3R expression on mast cells and eosinophils suggests that tagraxofusp may have the potential to diminish tumor bulk in addition to relevant underlying stem cell populations. The visible presence of plasmacytoid dendritic cell (pDC) nodular infiltrates in the bone marrow of a subset of chronic myelomonocytic leukemia (CMML) patients suggests a potential role of supporting dendritic cells within some of these neoplasia; preclinical data from other myeloid malignancies has indicated that targeting of these IL-3R expressing supporting cell populations may augment tagraxofusp antineoplastic effects observed against malignancies characterized by IL-3R expression ([Chauhan 2014](#)).

CD123 expression has been detected on CMML blasts, CMML monocytes, and leukemia stem cells in both MPNs and CMML ([Shen 2015](#), [Krishnan 2018](#)). In one study of 20 CMML patient samples, CD123 was found to be expressed at higher levels on blasts and monocytes compared to lymphocytes, which showed low to no expression ([Krishnan 2018](#)). Moreover, CD123 expression on both blasts and monocytes was higher in CMML-1 and CMML-2 patients relative to CMML-0 patients ([Krishnan 2018](#)). Another study assessing 118 CMML bone marrow samples by a validated multi-color flow cytometry immunophenotyping assay found that CD34+ blasts exhibited increased expression of CD123 in 64% of CMML patients compared to 3% of control patients ([Shen 2015](#)).

CD123 is also expressed on neoplastic pDCs in the tumor microenvironment of CMML ([Facchetti 2016](#), [Lucas 2019](#), [Vermi 2004](#), [Brunetti 2017](#), [Ji 2014](#), [Naresh 2010](#), [Vermi 2011](#)). These pDCs have been shown to share mutations with, and belong to, the malignant CMML clone ([Lucas 2019](#)). In particular, pDCs have been shown to share RAS pathway mutations with the CMML clone, which are associated with poor prognosis including a significant increase in the cumulative risk of AML transformation ([Lucas 2019](#)). Notably, RAS pathway mutations are associated with a higher fraction of pDCs in the bone marrow (> 5%) of patients with CMML and clinically manifest as proliferative disease ([Lucas 2019](#), [Ricci 2010](#)). Consistent with these findings, pDCs have been identified in the spleen of some patients with CMML, and it has been suggested that pDCs could serve as a therapeutic target in patients with CMML ([Lucas 2019](#), [Pophali 2018](#)).

1.1.2. Study Design

Study STML-401-0314 was initially designed as a 2-stage, non-randomized, open-label, multicenter study of tagraxofusp in patients with subtypes of advanced, high risk MPNs. Initially in this study, patients with CMML and myelofibrosis (MF), as well as systemic

mastocytosis (SM) and advanced symptomatic chronic eosinophilic leukemia, including primary eosinophilic disorders (PED) were eligible for enrollment.

In Stage 1, which is complete at the time of this Statistical Analysis Plan (SAP), only patients with CMML and MF were enrolled. The primary objective of Stage 1 was to establish the maximum tolerated dose (MTD) or the maximum tested dose (MTeD) at which multiple dose-limiting toxicities (DLTs) were not observed. In Stage 2, further characterization of the safety and initial assessment of clinical activity at the recommended phase 2 dose (RP2D) were intended in patients with MF and CMML, with an initial planned sample size of 18 patients in each cohort, then extended to approximately 30 patients in each cohort. Enrollment in Stage 2 is closed.

In Stage 1, 9 patients (5 with CMML and 4 with MF) received tagraxofusp at doses of [REDACTED] via intravenous (IV) infusion on days 1-3 every 21 days for Cycles 1-4, every 28 days for Cycles 5-7, and every 42 days for Cycles 8 and beyond. No MTD was identified in Stage 1 and the MTeD was 12 µg/kg which was considered the RP2D. In Stage 2 of this study, patients received tagraxofusp at the RP2D, 12 µg/kg, on the same schedule as Stage 1. Stage 2 primarily included patients with CMML and MF; 1 SM patient was treated during Stage 2 at the RP2D.

Based on preliminary clinical activity observed and increasing scientific and clinical knowledge of CMML, Stage 3A was added by protocol amendment 7, dated October 21, 2019. Stage 3A enrolled 2 populations of patients with CMML-1 and CMML-2:

1. Previously untreated patients who are high risk and not expected to benefit from hypomethylating agents (HMAs) (previously untreated patients; approximately 20 patients), and
2. Patients who are primary or secondary failures to first-line therapy, including HMAs, hydroxyurea (HU), or intensive chemotherapy (first-line failure patients; approximately 20 patients).

1.1.3. Study Objectives

This SAP is designed to outline the methods to be used in the analysis of study data in order to answer the study objective(s). Populations for analysis, data handling rules, statistical methods, and formats for data presentation are provided. The statistical analyses and summary tabulations described in this SAP will provide the basis for the results sections of the clinical study report (CSR) for this trial.

This SAP will also outline any differences in the currently planned analytical objectives relative to those planned in the study protocol.

1.1.3.1. Stage 1 Study Objectives

The primary objectives of Stage 1 of the study were to determine the MTD or the MeTD at which multiple DLTs are not observed of tagraxofusp and to characterize the safety profile of tagraxofusp. Stage 1 objectives are described in Protocol Amendments 6 and earlier.

1.1.3.2. Stage 2 Study Objectives

The secondary objectives for the study from Protocol Amendment 6 and earlier are to characterize the anti-tumor activity (including response rates, components of the response criteria, duration of response [DOR], progression-free survival [PFS], and overall survival [OS]), pharmacokinetic (PK), and immunogenicity of tagraxofusp.

An additional primary objective of Stage 2 is a preliminary assessment of response rates associated with SL-401 in each of the evaluated MPNs.

Specific components of the International Working Group Myeloproliferative Neoplasms Research and Treatment (IWG-MRT) consensus response criteria and additional clinical parameters for CMML will be assessed as secondary endpoints, including:

- Change in body weight (individual and median) over time.
- Change in hemoglobin (individual and median) over time.
- Change in Eastern Cooperative Oncology Group Performance Status (ECOG PS) (individual and median) over time.
- PFS (as defined in IWG-MRT consensus).
- OS.

Specific components of the IWG-MRT/ European LeukemiaNet consensus response criteria and additional clinical parameters for MF will be assessed as secondary endpoints, including but not limited to:

- Proportion of patients with reduction of $\geq 35\%$ in spleen volume at week 24 (postbaseline, as measured by magnetic resonance imaging [MRI] or computed tomography [CT]).
- Proportion of patients with reduction of $\geq 35\%$ in spleen volume at week 48 (postbaseline, as measured by MRI or CT).
- Proportion of patients (transfusion-dependent at baseline) who achieve transfusion independence (during any 12-week period following initiation of study therapy, as defined in IWG-MRT consensus).
- Proportion of patients who report a reduction in total symptom score of $\geq 50\%$ from baseline to week 24 (as assessed via the Myeloproliferative Neoplasm Symptom Assessment Form Total Symptom Score [MPN-SAF TSS]).
- Change in hemoglobin (individual and median) over time.
- Change in body weight (individual and median) over time.
- Change in ECOG PS (individual and median) over time.
- PFS (as defined in IWG-MRT/ELN consensus).

- OS.

Exploratory objectives are to characterize expression of IL-3R/CD123 (and other potentially relevant stem cell and disease markers) on myeloid malignant cells and associated cell populations in the bone marrow (BM) (when feasible), to evaluate potential changes in IL-3R/CD123 (and other potentially relevant marker) expressing populations over time, and preliminary correlation of baseline IL-3R/CD123 (and other potentially relevant markers) expression and clinical efficacy (including response rates).

Note that from Amendment 7 and later of the protocol, which focused on Stages 2 and 3a of the study, the objectives were not specific with regard to primary versus secondary objectives.

Objectives of Stage 2 in patients with CMML from Protocol Amendment 7 and later were:

- To characterize the safety profile of tagraxofusp.
- To obtain preliminary evidence of response to tagraxofusp therapy as assessed by the International Working Group (IWG) MDS consensus response criteria ([Cheson 2006](#)), and to obtain data relative to additional clinical parameters that may be used in determination of therapeutic benefit.

Objectives of Stage 2 in patients with MF from Protocol Amendment 7 and later were:

- To characterize the safety profile of tagraxofusp.
- To evaluate the potential efficacy of tagraxofusp based on evaluation of specific components of the IWG-MRT and European LeukemiaNet consensus response criteria ([Tefferi 2013B](#)) and additional clinical parameters.
- To collect clinical data and evaluate the activity of tagraxofusp in specific sub-populations of patients with MF that are of interest, including patients who have relapsed from or are refractory to treatment with a JAK inhibitor (JAKi), patients who are not candidates for treatment with JAKi (due to thrombocytopenia) and patients with concurrent monocytosis.

1.1.3.3. Stage 3A Study Objectives

Objectives of Stage 3A in patients with CMML are:

- To characterize the safety profile of tagraxofusp.
- To obtain preliminary evidence of response to tagraxofusp therapy as assessed by the MDS/MPN 2015 criteria ([Savona 2015](#)), with the addition of a stable disease (SD) category, and to obtain data relative to additional clinical parameters that may be used in determination of therapeutic benefit.

The MDS/MPN 2015 criteria ([Savona 2015](#)) represent the current consensus criteria for evaluation of clinical benefit in patients with CMML, beyond those specified in the IWG-MDS criteria ([Cheson 2006](#)). Thus, as an inherent component of the design of Stage 3A, responses to treatment are being assessed using the MDS/MPN 2015 criteria. The hematology community has recognized that a lack of a SD category in the 2015 MDS/MPN IWG criteria creates

considerable uncertainty in the categorization of patients on any CMML study. Therefore, a SD category, defined as those patients not belonging to any of the defined categories in the 2015 criteria, has been added as a response category.

The purpose of Stage 3A, is to analytically evaluate the clinical benefit derived from individual components, or variations thereof, of the MDS/MPN 2015 criteria that may allow for a prospective definition of a primary efficacy endpoint. Clinical benefit includes erythroid, platelet, neutrophil, spleen, and symptom responses, as defined in Table 8-4 in [Section 8.2](#), as well as transfusion dependence status and symptom score.

1.2. Study Design

1.2.1. Synopsis of Study Design

This is a non-randomized, open-label, multicenter study, divided into multiple stages.

1.2.1.1. Stage 1 Study Design

During Stage 1, approximately 12-36 patients were to be treated with tagraxofusp at doses of [REDACTED] /day for 3 consecutive days at the beginning of each 21-day cycle. Three to 6 patients were to be treated at each dose level. All patients within a cohort must have completed the first cycle of therapy before patients from a new cohort received tagraxofusp at the next higher dose. No intra-patient dose escalation was allowed. The first cohort of patients was to receive tagraxofusp at a dose of [REDACTED]. After all patients in this cohort completed the first cycle of therapy, the dose for the second cohort of patients was to increase by [REDACTED] to [REDACTED] /day, conditional on the DLT rules. Beginning with the [REDACTED] /day dose level of tagraxofusp, a decision to allow treatment at the next higher dose level would depend on the number of patients who experienced a DLT during the first cycle, as per the protocol. Expansion of the [REDACTED] /day cohort to up to 6 patients, if necessary, would follow the same rules as the [REDACTED] /day cohort. The same DLT rules also applied to the [REDACTED] /day, [REDACTED] /day, [REDACTED] /day, and [REDACTED] /day cohorts.

1.2.1.2. Stage 2 Study Design

Stage 2 was a non-randomized, open-label multicenter study stage to determine the safety and efficacy of single-agent tagraxofusp in patients with CMML and separately in patients with MF. Tagraxofusp was administered as a 15-minute IV infusion once daily on Days (D) 1 to 3 of a 21-day cycle (Cycles [C] 1 to 4); and on D1 to 3 of a 28-day cycle (C5 and beyond). The dosing period may have been extended for dose delays up to D10 of each cycle. Patients could continue to receive treatment with tagraxofusp as long as, in the opinion of the Investigator, benefit from treatment was indicated.

Beginning with Protocol Amendment 7, up to approximately 20-25 additional patients with MF were to be enrolled in Stage 2 to further elucidate the safety and efficacy profile of tagraxofusp in this patient population. Thus, across all study stages, approximately 50-55 patients with MF could be enrolled.

Note: CMML and MF patients consented and enrolled with Amendment 6 or prior, and currently on active treatment or in survival follow-up, continued to be followed according to the

schedule of events in Amendment 6. These patients were not reconsented under Amendment 7 or beyond.

1.2.1.3. Stage 3A Study Design

Stage 3A is a 2-arm, non-randomized, open-label multicenter study stage in patients with CMML intended to identify clinically important responses that connote clinical benefit and potential endpoints, as well as gather data on CD123 expression on pDCs and monocytes in CMML.

Stage 3A includes 2 populations of patients with CMML: those with CMML-1 or CMML-2 who are refractory/resistant/intolerant to HMs, or HU, or intensive chemotherapy; and patients with treatment naïve CMML-1 or CMML-2 with molecular features associated with a poor prognosis who are not expected to benefit from HMs.

In Stage 3A patients were administered tagraxofusp at a dose of [REDACTED] as a 15-minute IV infusion once daily on D1 to 3 of a 21-day cycle (C1 to C4) and then on D1 to 3 of a 28-day cycle (C5 and beyond). The dosing period may be extended for dose delays up to D10 of each cycle.

1.2.2. Randomization Methodology

As this is a single-agent study, randomization is not applicable.

1.2.3. Stopping Rules and Unblinding

Tagraxofusp treatment may be discontinued for any of the following reasons:

- Patient withdrawal of consent.
- Occurrence of unacceptable toxicity, including DLT.
- Tagraxofusp-related anaphylaxis or Grade ≥ 3 hypersensitivity reaction.
- Disease recurrence/progression.
- Intercurrent illness that prevents further administration of tagraxofusp.
- Patient non-compliance.
- Occurrence of pregnancy.
- Investigator's decision.

The reason for tagraxofusp discontinuation and the date of discontinuation was to be recorded in the electronic case report form (eCRF).

1.2.4. Study Procedures

The schedule of assessments, as outlined in the study protocol, is provided in [Section 7, Table 7-1](#), [Table 7-2](#), [Table 7-3](#), and [Table 7-4](#).

1.2.5. Efficacy, Pharmacokinetic, and Safety Parameters

1.2.5.1. Efficacy Parameters and Endpoints

Efficacy data from Stages 1 and 2 among patients treated at 12 ug/kg/day will be analyzed with descriptive statistical methods. Further details on the definitions and analysis methods for efficacy endpoints are provided in [Section 4.3](#). Refer to [Section 8](#) for detailed response criteria established for CMML and MF.

Primary Efficacy Endpoint:

The primary efficacy endpoint is investigator assessed objective response rate (ORR) for both CMML and MF. Objective response rate is defined as the number and percentage of patients who achieve disease-specific complete response (CR) or partial response (PR) after treatment.

Time to objective response and bridge to stem cell transplant after objective response will be assessed to support the primary efficacy endpoint.

Specific components of the IWG-MRT/ELN response criteria for defining clinical improvement for MF patients include anemia, spleen, and symptom responses. Specific components of the IWG-MRT response criteria for clinical benefit for CMML patients include erythroid, platelet, neutrophil, spleen, and symptom responses. The datapoints corresponding to each individual component of the responses will also separately be assessed and compared to baseline results for both MF and CMML patients as secondary endpoints. These include spleen volume, transfusion dependency, tumor symptoms score, blast results, absolute monocyte count results, white blood cell count results, hemoglobin results, and platelet results.

MF patients will be classified as “dependent” or “independent” at baseline for packed red blood cells (pRBC) if they received transfusions of at least 6 units in the 12 weeks prior to the study enrollment, for a hemoglobin level of < 85 g/L, in the absence of bleeding or treatment-induced anemia. In addition, the most recent transfusion episode must have occurred in the 28 days prior to study enrollment. Transfusion independence for MF will be defined as patients who experience at least a 12 week period during any point on treatment with no transfusion of that type required, including hemoglobin level of >=85 g/L.

CMML patients will be classified as “dependent” or “independent” at baseline within each category of platelets, packed red blood cells (pRBC), and both (i.e., receiving both platelets and pRBC) if they received transfusions of at least 4 units in the 8 weeks prior to the study enrollment. Transfusion independence for CMML will be defined as patients who experience at least a 8 week period during any point on treatment with no transfusion of that type required.

Secondary Efficacy Endpoints

The secondary efficacy endpoints are DOR, PFS, OS, and duration of follow-up.

Duration of objective response is defined as the time from when criteria are first met for CR or PR until the date that the criteria for relapse is met. Progression-free survival is defined as the time from the date of first infusion of tagraxofusp to the date of PD or death from any cause. Overall survival is defined as the time from the date of first infusion of tagraxofusp to the date of death from any cause.

1.2.5.2. Pharmacokinetic and Immunogenicity

Pharmacokinetics

A quality control check of the NCA will be conducted.

Per kg dose levels will be converted to actual doses using subject body weight. Actual administered doses will be used in the calculation of PK parameters.

If pre-dose PK concentrations on Day 3 will result not-measurable in most subjects and very low in the few subjects with measurable PK concentrations, then single-dose PK parameters will be estimated for each PK profile (Cycle 1 Day 1 (C1D1), Cycle 1 Day 3 (C1D3), Cycle 4 Day 1 (C4D1), and Cycle 4 Day 3 (C4D3)).

The following PK parameters will be calculated, as data permit:

Name	Description	Formula
C_{\max}	maximum observed concentration	
t_{\max}	time of first occurrence of C_{\max}	
t_{last}	time of last quantifiable concentration	
AUC_{last}	area under the concentration time curve from time = 0 to the last quantifiable observation	Calculated with the Linear Up/Log Down method: Linear trapezoidal method $AUC_{(t_1-t_2)} = (t_2 - t_1) \cdot (C_1 + C_2) / 2$ Logarithmic trapezoidal method $AUC_{(t_1-t_2)} = (t_2 - t_1) \cdot (C_2 - C_1) / \log_e(C_2/C_1)$
λ_z	first order terminal elimination rate constant	Estimated by linear regression of logarithmically transformed concentration versus time data

Name	Description	Formula
$t_{1/2}$	terminal elimination half-life	$\log_e(2)/\lambda_z$
AUC_{inf}	area under the concentration time curve from time = 0 extrapolated to infinity	$AUC_{last} + C_{last}/\lambda_z$ where C_{last} is the last observed quantifiable concentration
% AUC_{extrap}	Percentage of AUC_{inf} obtained by extrapolation	$AUC_{inf} - AUC_{last}/AUC_{inf} \cdot 100$
CL	total body clearance	$Dose/AUC_{inf}$
$MRT_{inf\ IV}$	mean residence time extrapolated to infinity	$AUMC_{last} + t_{last}(AUC_{inf} - AUC_{last})/AUC_{last} - TI/2$ where TI is the infusion duration, and AUMC _{last} is the area under the first moment of the concentration-time curve from time zero to the time of the last quantifiable concentration.
V_{ss}	steady state volume of distribution	$CL_{ss} \cdot MRT_{inf\ IV}$
V_z	volume of distribution during the disposition phase	CL/λ_z

The following rules will be used for λ_z calculation:

- (i) at least 3 non-zero time-points in the elimination phase for linear regression, excluding C_{max} ,
- (ii) adjusted R squared ≥ 0.8 ,
- (iii) span ≥ 2 .

When criteria (i) or (ii) for λ_z calculation will not be satisfied, both λ_z and related parameters (i.e. $t_{1/2}$, AUC_{inf} , V_z , CL, $MRT_{inf\ IV}$ and V_{ss}) will not be calculated. Cases where span < 2 will be flagged.

If $AUC_{extr} > 20\%$, AUC_{inf} and related parameters (i.e. $MRT_{inf\ IV}$ and V_{ss}) will not be reported.

AUC_{last} will be calculated and reported for subjects with at least 2 non-zero/BLQ time-points.

Missing concentration will be left missing for the calculation of summary concentration statistics and for the estimation of PK parameters.

All concentration results reported as below the limit of quantification (BLQ) will be set to zero.

Erroneous and physiologically implausible individual PK concentration values might be excluded from the estimation of PK parameters and from the calculation of summary concentration statistics. Excluded data will be listed with the reason for exclusion provided and will be flagged in the individual concentration listings.

Actual times from the start of the Tagraxofusp infusion and actual infusion durations will be used in the estimation of PK parameters. For records where the sample collection time is missing, the scheduled collection time will be used. For records where the calculated actual time from the start of Tagraxofusp infusion will result in a negative value, the actual time will be set to zero. For records where the actual infusion duration is missing, the scheduled infusion duration of 15 min will be used. For ease of data presentation, scheduled collection times will be used in tables and figures of PK concentration data.

PK concentrations collected in unscheduled visits will be excluded from the analysis.

Immunogenicity

Summary of immunogenicity parameters, including anti-drug antibodies (further characterized for specificity to Diphtheria Toxin and/or human interleukin-3 [hIL-3]), specific anti-hIL-3 antibodies, and tagraxofusp neutralizing antibodies will be performed. Further details on these analyses are provided in [Section 4.5](#).

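### SAP 1.2.5.2: the list of parameters withheld above 20% AUC extrapolation omits CL and Vz, and the MRT and Vss formulas are not in single-dose form

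*SAP*

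**What the plan says.** All of this is in the Pharmacokinetics part of SAP 1.2.5.2.

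- **Definitions.** The parameter table gives "total body clearance" as Dose/AUCinf, and "volume of distribution during the disposition phase" as CL/λz. The "steady state volume of distribution" is CLss × MRTinf IV. CLss appears nowhere else in the table.
- **MRT.** The "mean residence time extrapolated to infinity" is built from AUMClast, tlast(AUCinf - AUClast), a divisor AUClast, and a subtraction of TI/2.
- **Failed-λz rule.** If criterion (i) or (ii) fails, λz, t1/2, AUCinf, Vz, CL, MRT and Vss "will not be calculated. Cases where span < 2 will be flagged".
- **20% rule.** The next rule says that if the extrapolated share exceeds 20%, AUCinf "and related parameters (i.e" are not reported. Its list contains only MRT and Vss. The quoted words open the list in both rules; this point concerns the second.
- **Single-dose condition.** If Day 3 pre-dose concentrations are not measurable in most subjects and very low in the rest, "then single-dose PK parameters will be estimated for each PK profile". No second set of formulas is given for either outcome.

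**The concern.** CL and Vz depend on AUCinf just as MRT and Vss do. The failed-λz rule shows that the authors treat them as dependent, but the 20% rule leaves them out. A programmer working from the text would withhold AUCinf and still output CL. Dose divided by that CL returns the withheld AUCinf exactly. Summaries of CL and Vz would then mix accepted and rejected profiles, and CL and Vss would rest on different sets of profiles although Vss is a product of a clearance and MRT.

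The MRT expression is the steady-state form with tlast in place of the dosing interval τ. Applied to a single dose, it is biased whenever decline has more than one phase. Any error in MRT passes in proportion into Vss.

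**Working it through.** The plan states no figure to reproduce. The check has two parts.

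**Inputs.** TI = 0.25 h (SAP 1.2.5.2: "the scheduled infusion duration of 15 min will be used" where the actual duration is missing). The last sample is 240 minutes after the end of infusion (Protocol Table 2 and SAP Table 7-1, footnote 16: MF patients, Infusion 1 of Cycles 1 and 2), so tlast = 4 + 0.25 = 4.25 h from the start. The SAP also names Day 3 and Cycle 4 profiles, for which these documents give no sampling times; 4.25 h is an assumption there. The documents give no half-life, so all disposition parameters below are assumptions (times in h, rate constants per h).

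**Part 1: which parameters carry the extrapolated area.** AUCinf = AUClast + Clast/λz. CL = Dose/AUCinf. Vz = CL/λz = Dose/(AUCinf·λz). All three contain Clast/λz. For a one-compartment infusion with rate constant k, the extrapolated share is [(1 - e^(-0.25k))/(0.25k)]·e^(-4k):

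| Assumed half-life | k | Extrapolated |
|---|---|---|
| 1 h | 0.693 | 5.7% |
| 1.75 h | 0.396 | 19.5% |
| 2 h | 0.347 | 23.9% |
| 3 h | 0.231 | 38.6% |

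The 20% limit is passed at a half-life between 1.75 and 2 h, or earlier if the last quantifiable sample comes before 4.25 h.

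**Part 2: MRT.** Brackets and fraction bars may have been lost when the PDF was read, so I use the most favourable reading.

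- SAP form: [AUMClast + tlast(AUCinf - AUClast)]/AUClast - TI/2.
- Single-dose form: AUMCinf/AUCinf - TI/2, with AUMCinf = AUMClast + tlast·Clast/λz + Clast/λz².

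For a mono-exponential bolus the SAP form is exact. With T = tlast, its numerator is [1 - e^(-kT)(1 + kT)]/k² + T·e^(-kT)/k = (1 - e^(-kT))/k². Dividing by AUClast = (1 - e^(-kT))/k gives 1/k. With a 15-minute infusion it is +0.1% at a half-life of 0.5 h and +1.2% at 1.75 h, the longest of the half-lives tried that stays below 20% extrapolation.

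A worked bi-exponential case has A = 1, α = 3, B = 0.1, β = 0.35, tlast = 4.25 h. Numerical integration gives AUClast = 0.5516, AUMClast = 0.5254 and Clast = 0.02362.

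- Clast/λz = 0.02362/0.35 = 0.0675. AUCinf = 0.6191. Extrapolated share = 0.0675/0.6191 = 10.9%, so MRT is reportable.
- SAP form: (0.5254 + 0.2868)/0.5516 - 0.125 = 1.347.
- Single-dose form: (0.5254 + 0.2868 + 0.1928)/0.6191 - 0.125 = 1.498.
- Error: 1.347/1.498 - 1 = -10.1%.

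Other assumed profiles, error relative to the single-dose form:

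| A, α, B, β | tlast | Extrapolated | MRT error |
|---|---|---|---|
| 1, 3, 0.3, 0.7 | 4.25 h | 3.1% | -1.2% |
| 1, 4, 0.2, 0.5 | 4.25 h | 7.8% | -3.5% |
| 1, 3, 0.3, 0.7 | 2 h | 15.8% | -6.6% (0.900 v 0.964) |
| 1, 4, 0.2, 0.5 | 3 h | 14.6% | -7.1% |

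Changing only the divisor to AUCinf does not repair the formula. The worked case and the last two rows would then be 21% to 23% too low, because Clast/λz² is still missing.

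**The case against.** **CL and Vz.** A reader might infer that the SAP commits to reporting them from rejected profiles. It does not say so. The 20% rule withholds AUCinf and parameters related to it, and the sentence before names CL and Vz as related, so an experienced pharmacokineticist might well withhold them. The authors may have meant the list as examples. A quality control check of the non-compartmental analysis is also planned. What stands is that the list is closed as written, that neither document suppresses CL or Vz elsewhere for this reason, and that quality control against an incomplete rule would pass the incomplete output.

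**MRT.** A reader might infer that the formula is wrong for the planned analysis without qualification. The single-dose analysis is conditional on negligible Day 3 pre-dose levels, and the formula and CLss look like steady-state notation. That is a fair reading of their origin. It leaves the single-dose branch, which the plan itself foresees, without correct formulas.

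**Size.** A reader might take 7% or 10% as the expected MRT error. Nothing in the documents supports a particular value: the same two profiles give -6.6% and -7.1% with a last quantifiable sample at 2 or 3 h, but -1.2% and -3.5% at 4.25 h. Larger errors in the examples run (-12.4% and -22.3%) occur at 23.8% and 24.1% extrapolation, where MRT and Vss are already withheld.

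**Weight.** PK is summarised descriptively (SAP 4.6). The only parameters given distribution plots, Cmax and AUClast, are untouched. No dose, efficacy or safety decision in the documents uses CL, Vz, MRT or Vss.

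**Conclusion.** Both points hold as defects of specification. The 20% rule is incomplete: read literally, it lets CL and Vz through from an AUCinf that the plan has rejected. The MRT formula is not the single-dose form under any bracketing, and Vss relies on an undefined clearance.

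In any profile affected by the first point, more than a fifth of the AUC behind CL is unobserved. How many profiles that is cannot be told from the documents, and it may be none. For the second, with sampling to 4.25 h and extrapolation of 20% or less, the error is +0.1% to +1.2% for mono-exponential decline and about -1% to -10% in the bi-exponential examples. These are scenarios under assumed disposition, not estimates for tagraxofusp. The consequence is confined to descriptive PK tables and listings, so this is a minor correction worth making before the outputs are programmed.

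**What to change.** In SAP 1.2.5.2:

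1. Add CL and Vz to the parameters not reported when the extrapolated share exceeds 20%.
2. For single-dose profiles, define MRTinf IV = AUMCinf/AUCinf - TI/2, with AUMCinf = AUMClast + tlast·Clast/λz + Clast/λz².
3. Replace CLss by CL in the Vss formula.
4. State which formulas apply if the Day 3 pre-dose condition is not met.

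These are short text edits. They need no new data, since Clast and λz are already required for AUCinf. The cost is that CL and Vz will be available for fewer profiles, as the plan's own 20% criterion already implies.
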